**Statistical Methods (Continued):****Efficacy (Continued):**

If the minimum number of days of diary data (i.e., 4 days for SF and AP) are not available, then the subject's score for that visit will be considered missing and NRI will be used for any endpoints (e.g., clinical remission) relating to data for this visit. Subjects who discontinue prior to Week 16 for any reason will be considered as "not-achieved" for clinical remission endpoint.

The following sensitivity analyses for the primary endpoint of clinical remission will be conducted:

- An analysis of observed cases, which excludes those subjects with missing SF or AP data at scheduled assessment visits.
- The primary analysis will be repeated using mixed-imputation. Subjects who discontinue prior to Week 16 due to lack of efficacy or adverse events will be considered as "not achieved" for the clinical remission. Subjects who discontinue for other reasons will be categorized according to LOCF.

The dose-response relationships using the most significant model in MCPMod among the five ABT-494 treatment groups and placebo group will be characterized for the primary endpoints endoscopic remission at Week 12/16 and clinical remission at Week 16. The response function will be the log odds (logit) of the proportion of subjects with endoscopic/clinical remission. The fitted curve will be shown graphically with confidence intervals for each dose. Estimates of the treatment differences in the response function and associated 95% confidences for each active dose against placebo will be calculated from the most significant model, as well as the average of all significant models. These results will be back-transformed to give point estimates of the difference in proportions and associated 95% confidence intervals.

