10.0 Efficacy Analysis

10.1 General Considerations

All statistical tests will be two-sided with the significance level of 0.100. Descriptive statistics will be provided. These include the number of observations, mean, standard deviation, minimum, median, and maximum for continuous variables; and number and percent for discrete variables. The analysis will be performed using SAS® (SAS Institute Inc., Cary, NC, USA).

Dose Response Modeling

Other than estimating the relative treatment effect of the investigational compound ABT-494 to placebo, one important goal of this Phase 2 study is to establish dose-response relationship to facilitate the dose selection for future Phase 3 trials. Multiple Comparison Procedure and dose-response Modeling (MCPMod) with a pre-defined group of candidates dose response curves will be tested against flat dose-response curve to best characterize the dose-response relationship.

Steps of MCPMod:

1. Choose a candidate set of S models.
2. Compute the optimum contrast for each model.
3. Use contrast test to find the significant T models while preserving FWER (one-sided significant level of 0.05).

4. Use AIC criteria to find the most significant model from the significant T models found from Step 3.
5. Use the model found from Step 4 to fit observed data from the study and make inference (e.g., to find Minimum Effective Dose (MED) or the dose achieving certain amount of maximum effect), or use all significant models to make inference about the weighted target dose of interest.

ADDPLAN or R will be used to evaluate different dose-response models and to make dose recommendation.

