10.2 Primary Efficacy Analyses

This section provides the details of the primary efficacy analysis for the study.

Co-Primary Efficacy Variables:

- Proportion of subjects who achieve endoscopic remission at Week 12/16.
- Proportion of subjects who achieve clinical remission at Week 16.

Analysis Data Set for the Primary Efficacy Analysis:

The primary efficacy analysis will use the MITT analysis data set.

Imputation Method Used for the Primary Efficacy Analysis:

Missing average daily stool frequency or average daily abdominal pain at Week 16 or SES-CD at Week 12/16 will be imputed using the non-responder imputation (NRI) approach.

Statistical Method of the Primary Efficacy Analysis:

The dose-response relationships among the five ABT-494 treatment groups and placebo group will be characterized for the primary endpoints endoscopic remission at Week 12/16 and clinical remission at Week 16 using MCPMod approach. The following

models will be considered: linear, E_{max} , exponential, logistic, sigEmax, and quadratic. The MCPMod approach for trial analysis stage consists of two main steps: MCP and Mod step. The MCP step focuses on establishing evidence for a drug effect across the doses, i.e., detecting a statistically significant dose response signal for the clinical endpoint and patient population investigated in the study. This step will typically be performed using an efficient test for trend, adjusting for the fact that multiple candidate dose response models are being considered. If a statistically significant dose response signal has been established, one proceeds with determining a reference set of significant dose response models by discarding the non-significant models from the initial candidate set.

The response function will be the log odds (logit) of the proportion of subjects with endoscopic/clinical remission. The fitted curve will be shown graphically with confidence intervals for each dose. Estimates of the treatment differences in the response function and associated 95% confidences for each active dose against placebo will be calculated from the model. These results will be back-transformed to give point estimates of the difference in proportions and associated 95% confidence intervals.

Sensitivity Analysis of the Primary Efficacy Variables

The following sensitivity analyses for the primary endpoint of endoscopic remission will be conducted:

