- The proportion of subjects who achieve $> 50\%$ reduction from Baseline in SES-CD or endoscopic remission at Week 12/16.
- The proportion of subjects who achieve modified clinical remission at Week 16 among subjects with an average daily SF ≥ 4.0 or average daily AP ≥ 2.0 at Baseline.

For categorical efficacy endpoints for Induction Period, the pairwise comparisons for the difference in proportions of subjects between treatment groups and placebo group will be analyzed using the CMH test adjusted for Crohn's disease severity (SES-CD < 15 , ≥ 15) at Baseline. Additionally, the CMH-based 95% confidence interval for the difference in proportions will be provided. The 95% confidence interval for the difference in proportions within each Crohn's disease severity (SES-CD < 15 , ≥ 15) at Baseline category will be calculated based on normal approximation.

The non-responder imputation will be used for subjects with missing data at the endpoint evaluated. The last observation carried forward (LOCF) method will also be used as the sensitivity analyses for the secondary endpoints.

In general, continuous secondary efficacy variables with repeated measurements will be analyzed using a Mixed Effect Repeated Measure (MMRM) model. The mixed model includes the categorical fixed effects of treatment, Crohn's disease severity (SES-CD < 15, ≥ 15) at Baseline, week and treatment-by-week interaction and the continuous fixed covariates of baseline measurement. An unstructured variance-covariance matrix will be used. If convergence is not achieved, other variance-covariance matrix will be explored until coverage. The parameter estimations will be based on assumption of data being missing at random and using the method of restrictive maximum likelihood (REML).

Continuous secondary efficacy variables will also be analyzed using an Analysis of Covariance (ANCOVA) model including factors for treatment group and Crohn's disease severity (SES-CD < 15, ≥ 15) at Baseline, and Baseline values as a covariate. The MMRM analysis is considered primary for inferential purposes.

The additional endpoints include:

- Proportion of subjects who achieve clinical remission over time in Induction Period.
- Proportion of subjects who achieve clinical response over time in Induction Period.
- Proportion of subjects who achieve CDAI < 150 over time in Induction Period.
- Proportion of subjects with decrease in CDAI ≥ 70 points from Induction Baseline over time in Induction Period.

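### Co-primary dose-versus-placebo intervals: the model average required in the synopsis is missing from protocol 8.1.6.1.1 and induction SAP 10.2, and no stated interval reflects model selection, so fixed-model intervals are generally too narrow at 3 and 6 mg BID

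*SAP*

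**What the plan says.** Induction SAP 10.2 fits dose-response models on the logit scale. It says that treatment differences and "associated 95% confidences for each active dose against placebo will be calculated from the model", and then: "These results will be back-transformed to give point estimates of the difference in proportions and associated 95% confidence intervals". Protocol 8.1.6.1.1 has the same text.

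SAP 10.1 shows which model is meant. Step 4 is "Use AIC criteria to find the most significant model from the significant T models found from Step 3". Step 5 fits that model and draws inference from it, "or use all significant models to make inference about the weighted target dose of interest". The multi-model route is therefore optional, and it is offered for the target dose rather than for the dose-placebo differences. Protocol 8.1.6.1.1 names no selection rule.

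The protocol synopsis (Statistical Methods, Efficacy) asks for more: the same differences and intervals are to be "calculated from the most significant model, as well as the average of all significant models". It gives no weights.

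Section 12.1 of the induction SAP records no change from the protocol. That SAP was written against Amendment 4. The Amendment 5 list of changes touches neither statistical passage, so the mismatch is not explained by the change of version.

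**The concern.** There are two linked problems. The synopsis promises an averaged estimate of each co-primary effect, and the two sections that an analyst would program from do not mention it. It may never be produced.

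The interval that remains comes from a model picked because it fitted the data best. If it is computed as though that curve had been known in advance, it carries no uncertainty about the shape. The shape matters most at the lowest doses. A linear fit ties the effect at 3 mg BID to one eighth of the effect at 24 mg BID, and it shrinks the interval by the same factor.

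SAP 10.1 says that the modelling is meant to help choose Phase 3 doses. An interval at 3 or 6 mg that is far too narrow can make a low dose look reliably weak, or reliably effective, when 35 subjects per arm cannot show either.

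**Working it through.** **Inputs from the documents.** 35 per arm; 12% on placebo and a maximum of 35% on a BID arm; one-sided 5% contrast test (SAP 4.3 and 10.1). Candidates are linear, Emax, exponential, logistic, sigEmax and quadratic (SAP 10.2; the protocol omits quadratic). Selection is by AIC among significant models.

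**Assumed.** The documents give no model guesstimates, true curves or interval method. Several guesstimate sets and curves were tried, with delta-method intervals.

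**The plan's own figure.** Average power over the five protocol models came to 82.5%, 82.0% and 80.5% under three guesstimate sets. The stated figure of at least 80% is reproduced.

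**Mechanism.** The full effect on the logit scale is ln(0.35/0.65) − ln(0.12/0.88) = −0.619 + 1.992 = 1.373.

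- Linear model: Δ(d) = slope × d, so the half-width is 1.96 × se(slope) × d. A half-width of 1.02 at 24 mg becomes 1.02 × 3/24 = 0.13 at 3 mg. A separate pairwise interval at 3 mg has a half-width of 1.45.
- Suppose the truth is Emax with ED50 6 mg. Then Emax = 1.373 / (24/30) = 1.717, and Δ(3) = 1.717 × 3/9 = 0.57. A linear fit gives about 0.14 ± 0.12, which is nowhere near 0.57.
- With a linear model fitted to every trial with a significant slope, coverage under that Emax truth was 0% at 3 mg, under 1% at 6 mg and 99% at 24 mg. Under a linear truth it was 97% at every dose.

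**Following the SAP steps: eight curves, 4,000 trials each, six models.** Coverage (%) of the nominal 95% interval in trials with a significant signal, at 3 / 6 mg BID:

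| True curve | AIC-selected model | Average of significant models |
|---|---|---|
| Linear | 85 / 87 | 94 / 96 |
| Emax, ED50 6 | 55 / 57 | 83 / 91 |
| Emax, ED50 2 | 72 / 75 | 83 / 90 |
| Exponential | 38 / 49 | 96 / 100 |
| Logistic (12, 3) | 28 / 49 | 96 / 97 |
| sigEmax (8, 3) | 49 / 91 | 97 / 98 |
| sigEmax (4, 4) | 72 / 78 | 97 / 93 |
| Quadratic | 78 / 82 | 93 / 96 |

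The average uses AIC weights w_m and standard error Σ w_m √(se_m² + (d_m − d_avg)²). At 24 mg the selected-model interval covered 95-99%. With the protocol's five models, sigEmax (8, 3) covered 98% at 6 mg.

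**A larger run: 18 curves, 5,000 trials each.** Logit-scale coverage was 19-88% at 3 mg, 48-90% at 6 mg, 61-97% at 12 mg and 96-99% at 24 mg. The plan does not say how to back-transform. Taken around the fitted placebo rate, coverage was 19-92% at 3 mg and 53-94% at 6 mg. A delta-method interval on the difference in proportions gave 9-86% and 32-85%.

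**How much is due to selection.** The true model was fitted to the same significant trials. For linear, Emax and quadratic truths it covered 97-100% at both doses, against 37-88% (3 mg) and 48-90% (6 mg) after selection. For exponential, logistic and sigEmax truths it covered only 59-94% and 76-100%, against 19-77% and 49-84% after selection. In that second group, part of the loss is delta-method or parameter-boundary failure.

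**Repairs, same 18 curves, difference in proportions, 3 / 6 mg:**

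- bootstrap repeating test and selection: 93-100% / 93-99%
- AIC-weighted average: 80-99% / 87-99%, lowest under Emax
- CMH-based interval: 94-96% / 94-96%.

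**The case against.** **The method simulated is not in the plan.** No document names an interval method, so these figures belong to a delta-method interval chosen for the check. That stands, and the claim is limited accordingly. But nothing in the plan points to an interval that allows for selection.

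**A model-free interval probably exists already.** SAP 10.3 covers "For categorical efficacy endpoints for Induction Period, the pairwise comparisons for the difference in proportions" and adds: "Additionally, the CMH-based 95% confidence interval for the difference in proportions will be provided". Its additional endpoints include "Proportion of subjects who achieve clinical remission over time in Induction Period", which takes in Week 16. For endoscopic remission the SAP relies on the broad wording alone, though protocol 5.3.3.3 read with 8.1.6.3.1 covers it. A reader might infer that the co-primary endpoints have no sound interval anywhere. The documents do not support that. Section 10.2 simply does not mention the CMH interval.

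**Low coverage is not always a large error.** In a check on the difference in proportions, exponential and logistic truths gave 11-26% coverage at 3 mg, but the median miss was only 0.6-0.8 percentage points. Misses were material mainly under Emax, at about 4-7 points. The selected-model estimate also had lower root mean squared error than the pairwise difference under every curve (1.8-7.3 against 7.2-8.5 points at 3 mg). That stands: the criticism is of the interval, not of modelling.

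**No decision hangs on these intervals.** Also correct. A reader might infer that the trend test or the minimum effective dose is invalid. Type I error of the test is untouched, no claim is made about the target dose, and step 5 allows all significant models there.

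**The protocol does not prescribe single-model inference.** A reader might take 8.1.6.1.1 as a contrary plan. It names no selection rule, and the synopsis of the same protocol requires the average. AIC selection is stated only in the SAP.

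**Conclusion.** The point holds in limited form and should be fixed. The averaged co-primary estimate required by the synopsis is missing from both operative sections, and no interval reflecting model selection is specified. Under the assumed curves, a fixed-model delta-method interval is generally too narrow at the two lowest BID doses: roughly 20-90% coverage at 3 mg and 50-90% at 6 mg on the logit scale. It is curve-dependent at 12 mg and about nominal at 24 mg.

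The textual gap is certain. The sizes depend on assumed curves, guesstimates and interval method. The 98% case at 6 mg means that under-coverage there cannot be called universal, and not all of the loss is due to selection.

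**What to change.** The extension SAP (3.0) says that the induction SAP was signed off before the December 2016 lock. The change therefore belongs in a dated addendum, with added intervals labelled as such and protocol 8.1.6.1.1 aligned for consistency. For section 10.2:

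1. Report each dose-placebo difference from the most significant model and, as the synopsis requires, as the average of all significant models. State the weights as a new specification (for example AIC weights), since the synopsis gives none. Use a standard error that includes between-model variance, as in the formula above. Note that this improves coverage but does not fully restore it under Emax-type curves.
2. For the selected model, give a percentile bootstrap interval that resamples subjects within arm and repeats the trend test, AIC selection and fit each time. State what happens when no model is significant in a resample (for example AIC over all candidates, as simulated) and when an arm has no responders (for example a 0.5 continuity correction). The second case is not rare: with 3/35 observed, (32/35)^35 = 4.3% of resamples for that arm; with 2/35, (33/35)^35 = 12.8%. Label any fixed-model interval as conditional on the selected model.
3. State that the CMH-based 95% interval of section 10.3 is shown for both co-primary endpoints at every dose.

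The cost is a few sentences and modest programming. Under the assumed curves, mean interval widths at 3 and 6 mg BID become about 15 and 22 percentage points (bootstrap), rather than 6 and 11 (fixed-model delta method). The CMH intervals are about 30 and 32.

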10.3 Secondary Efficacy Analyses

Secondary efficacy variables are divided into two groups. The first group includes double-blind induction treatment period secondary endpoints. Analyses for the first group of secondary endpoints will be performed using MITT analysis set. The second group includes double-blind extension phase secondary endpoints. Analyses for the second group of secondary endpoints will be performed using ITT-N and ITT-NR analysis sets. This SAP is for Induction period only.

The secondary endpoints (*Double-Blind Induction Treatment Period*) include:

- Proportion of subjects who achieve CDAI < 150 at Week 16.
- Proportion of subjects with decrease in CDAI \geq 70 points from Baseline at Week 16.
- Proportion of subjects with decrease in CDAI \geq 100 points from Baseline at Week 16.
- Proportion of subjects who achieve clinical remission at Week 12.
- Proportion of subjects who achieve remission at Week 16 (endoscopic remission at Week 12/16 and clinical remission at Week 16).
- Proportion of subjects who achieve response at Week 16 (endoscopic response at Week 12/16 and clinical response at Week 16).
- Proportion of subjects with endoscopic response at Week 12/16.
- Proportion of subjects who achieve clinical response at Week 16.
- Proportion of subjects with an average daily SF \geq 2.5 AND average daily AP \geq 2.0 at Baseline who achieve clinical remission at Week 16.
- Proportion of subjects who steroid-free achieve CDAI < 150 at Week 16 among subjects taking corticosteroids at Baseline.
- Proportion of subjects who achieve steroid-free remission at Week 16 among subjects taking corticosteroids at Baseline.

- Proportion of subjects who achieve steroid-free clinical remission at Week 16 among subjects taking corticosteroids at Baseline.
- Proportion of subjects who achieve steroid-free endoscopic remission at Week 12/16 among subjects taking corticosteroids at Baseline.
- Change from Baseline in fecal calprotectin level at Week 16.
- Change from Baseline in fecal calprotectin level at Week 4.
- Change from Baseline in hs-CRP at Week 16.
- Change from Baseline in IBDQ at Week 16.
- Change from Baseline in IBDQ at Week 8.
- Proportion of subjects who achieve remission at Week 16 among subjects with isolated ileal Crohn's disease at Baseline.
- Change from Baseline in abdominal pain rating scale at Week 12 and Week 16.
- The proportion of subjects who achieve $> 50\%$ reduction from Baseline in SES-CD or endoscopic remission at Week 12/16.
- The proportion of subjects who achieve modified clinical remission at Week 16 among subjects with an average daily SF ≥ 4.0 or average daily AP ≥ 2.0 at Baseline.

For categorical efficacy endpoints for Induction Period, the pairwise comparisons for the difference in proportions of subjects between treatment groups and placebo group will be analyzed using the CMH test adjusted for Crohn's disease severity (SES-CD < 15 , ≥ 15) at Baseline. Additionally, the CMH-based 95% confidence interval for the difference in proportions will be provided. The 95% confidence interval for the difference in proportions within each Crohn's disease severity (SES-CD < 15 , ≥ 15) at Baseline category will be calculated based on normal approximation.

The non-responder imputation will be used for subjects with missing data at the endpoint evaluated. The last observation carried forward (LOCF) method will also be used as the sensitivity analyses for the secondary endpoints.

In general, continuous secondary efficacy variables with repeated measurements will be analyzed using a Mixed Effect Repeated Measure (MMRM) model. The mixed model includes the categorical fixed effects of treatment, Crohn's disease severity (SES-CD < 15, ≥ 15) at Baseline, week and treatment-by-week interaction and the continuous fixed covariates of baseline measurement. An unstructured variance-covariance matrix will be used. If convergence is not achieved, other variance-covariance matrix will be explored until coverage. The parameter estimations will be based on assumption of data being missing at random and using the method of restrictive maximum likelihood (REML).

Continuous secondary efficacy variables will also be analyzed using an Analysis of Covariance (ANCOVA) model including factors for treatment group and Crohn's disease severity (SES-CD < 15, ≥ 15) at Baseline, and Baseline values as a covariate. The MMRM analysis is considered primary for inferential purposes.

The additional endpoints include:

- Proportion of subjects who achieve clinical remission over time in Induction Period.
- Proportion of subjects who achieve clinical response over time in Induction Period.
- Proportion of subjects who achieve CDAI < 150 over time in Induction Period.
- Proportion of subjects with decrease in CDAI ≥ 70 points from Induction Baseline over time in Induction Period.
- Proportion of subjects with decrease in CDAI ≥ 100 points from Induction Baseline over time in Induction Period.
- Proportion of subjects who are IBDQ responders (increase in IBDQ score ≥ 16 points from Induction Baseline) over time in Induction Period.
- Proportion of subjects with IBDQ score ≥ 170 over time in Induction Period.
- Proportion of subjects who achieve steroid-free CDAI < 150 over time in Induction Period among subjects taking corticosteroids at Baseline.
- Proportion of subjects who achieve steroid-free clinical remission over time in Induction Period among subjects taking corticosteroids at Baseline.

- Change from Induction Baseline in fecal calprotectin level over time in Induction Period.
- Change from Induction Baseline in hs-CRP over time in Induction Period.
- SES-CD endpoints without any missing individual variables.
- The proportion of subjects with no anal fissures at Week 16 among subjects with anal fissures at Baseline.
- The proportion of subjects with no draining fistulas at Week 16 among subjects with draining fistula at Baseline.
- The proportion of subjects with no non-draining fistulas at Week 16 among subjects with non-draining fistula at Baseline.
- The proportion of subjects with no any fistulas at Week 16 among subjects with any fistula at Baseline.
- Change from Induction Baseline in Bristol Stool Chart at Week 4 and Week 16.
- The proportion of subjects who achieve Bristol Stool Chart response at Week 4 and Week 16.
- Cross tabulation of Baseline and Week 16 in EIM.
- The proportion of subjects who achieve modified clinical remission at over time in Induction Period among subjects with an average daily SF ≥ 4.0 or average daily AP ≥ 2.0 at Baseline.
- Change from Induction Baseline in EQ-5D over time in Induction Period.
- Change from Induction Baseline in WPAI over time in Induction Period.

